02.05.2018

Title

Treatment of Newly Diagnosed Gastroesophageal Reflux Disease in a National Population-based Cohort

Aim

To compare rate of surgery with medical treatment in patients with newly diagnosed gastro-esophageal reflux disease in a nationwide population based cohort over 15 years.

Background

Episodic reflux of gastric contents to the esophagus is physiological but is considered gastroesophageal reflux disease (GERD) when accompanied by bothersome symptoms, typically heartburn, regurgitation or retrosternal pain. Extra-esophageal symptoms such as asthma, laryngitis and chronic cough may also occur (1). GERD is a complex and multifaceted disease (2, 3), affecting 10-20% of the Western population (4) and has been shown to significantly reduce the quality of life (5). Worldwide, the prevalence of GERD has been increasing (6–8). Treatment of GERD consists of anti-secretory drugs, mainly proton pump inhibitors (PPI), or anti-reflux surgery. Laparoscopic anti-reflux surgery is considered standard of care in surgical treatment of gastro-esophageal reflux disease (9) and with careful patient selection based on thorough preoperative workup (10), symptom control and patient satisfaction are high compared to medical therapy. This has previously been demonstrated in metaanalysis (11, 12).

From 1990-2000 the utilization of anti-reflux surgery in the USA rose to 16.7 procedures per 100.000 inhabitants with a concomitant rise in the use of the transabdominal laparoscopic approach. This resulted in a decline of perioperative mortality and morbidity (13, 14). The rate of anti-reflux surgery dropped to 6.1 procedures per 100.000 inhabitants in 2010, when the patients were now older with significantly higher levels of comorbidity. Despite this, length of stay, morbidity and mortality was reduced even further. The laparoscopic approach is used in 80% of American procedures and the rate has not changed during the last ten years. It is unknown whether Denmark follows the same trends, as the popularity of anti-reflux surgery has been somewhat limited and the surgical setup is different with significantly fewer centers. In a Danish study, investigating the rate of reoperative anti-reflux surgery from 1997-2005, the rate of primary surgery was 5.2 per 100.000 inhabitants with a reoperation rate of 5% (15), however no data has been presented after 2005, and no Danish study has focused on treatment of newly diagnosed patients suffering from reflux disease.

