As such, it is currently unknown how many patients each year are given the diagnosis GERD after upper endoscopy in Denmark and what treatment they receive. It is also unknown how the utilization of medical and surgical treatment has developed in this group of patients.

Methods

The study is a register-based cohort study with data from Danish national health registries (The National Patient Registry, The Danish National Prescription Register and The Civic Registry). The study period is 2000-2015.

The study population consists of all adult Danish patients diagnosed with GERD and GERD-related diagnosis identified with ICD-10 codes DK20.9B, DK21.0-21.9B & DK22.7 using The National Patient Registry).To

02.05.2018

validate GERD-diagnosis, upper endoscopy must have been performed no more than three months before time of diagnosis for the patient to be included. Endoscopy must have been performed during the study period 2000-2015.

Patients with GERD and GERD-related diagnosis up to four years before upper endoscopy are excluded from the study as are patients with any diagnosis of cancer of the gastrointestinal tract 4 years prior to upper endoscopy to the end of follow-up.

Age, sex and Charlson Comorbidity Index at date of primary upper endoscopy are derived from the National Patient Registry. From the same source, any anti-reflux surgery (Nomesco: KJBC00, KJBC01, KJBC02, KJBW96, KJBW97) performed within two years of inclusion are identified.

From The National Prescription Register, data on medical treatment with any antacid and anti-secretory treatment (ATC: MA02B) are identified from 4 years before inclusion to 2 years after. Data on anti-thrombotic drugs and non-steroid anti-inflammatory drugs (ATC: MB01A & MM01A) are also retrieved for the same period to adjust for possible preventive therapy with anti-secretory drugs. From the Civic Register, data on mortality in the follow-up period are retrieved.

Statistical analysis

Data will be analyzed using STATA15. Descriptive analysis of age, sex, Charlson Comorbidity Index, mortality and rate of anti-thrombotic treatment comparing patients treated pharmacologically (in defined daily dosages per year) or surgically (any anti-reflux procedure) for reflux disease using Student's t-test, Chi2-test and Mann-Whitney-U test.

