Logistic and multinomial regression will be performed with treatment type (pharmacological, surgical or none) as primary outcome and age, sex, Charlson Comorbidity Index, pharmacological anti-reflux treatment prior to diagnosis, antithrombotic treatment and year of diagnosis as independent variables.

Secondary analysis will be performed using Cox-regression investigating time to initiation of any treatment with age, sex, Charlson Comorbidity Index, pharmacological anti-reflux treatment prior to diagnosis, antithrombotic treatment and year of diagnosis as independent variables. Change in treatment rates over time will also be investigated using national Danish census data and Poisson regression.

Sensitivity analysis excluded patients with anti-thrombotic treatment will be performed.

Funding and Ethical considerations

The study is part of a ph.d. thesis and is funded by The Region of Southern Denmark, The University of Southern Denmark, The Department of Surgery, Kolding Hospital and The Research Council at Little Belt Hospital.

The study requires no informed consent in Danish law as the study is register-based. However, permission from The Danish Data Protection Agency and The Danish Health Data Agency will be obtained before the study is commenced.

None of the involved parties have financial interests or conflicts of interest pertaining to this study.

References

1. Madanick RD. Extraesophageal presentations of GERD: where is the science? *Gastroenterol Clin North Am.* 2014;43:105-120.

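### The secondary Cox model of treatment initiation keeps prior anti-reflux drug users without a drug-free window, so a refill can count as a start and bias the hazard ratios in either direction

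*Combined protocol and SAP*

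**What the plan says.** The Aim is "To compare rate of surgery with medical treatment in patients with newly diagnosed gastro-esophageal reflux disease". The primary regression takes "treatment type (pharmacological, surgical or none) as primary outcome". The secondary one is a "Cox-regression investigating time to initiation of any treatment with age, sex, Charlson Comorbidity Index, pharmacological anti-reflux treatment prior to diagnosis"; antithrombotic treatment and calendar year are the remaining covariates. The plan does not define initiation and does not state the Cox time origin.

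The Methods section sets the eligibility rules. On earlier disease it says: "Patients with GERD and GERD-related diagnosis up to four years before upper endoscopy are excluded from the study". Gastrointestinal cancer is also excluded, but earlier anti-reflux medication is not. Dispensings of antacid and anti-secretory drugs (MA02B) "are identified from 4 years before inclusion to 2 years after". This history is not used to decide who can initiate. The one sensitivity analysis removes patients on antithrombotics, not prior anti-reflux drug users.

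Two dates could serve as time zero. For inclusion, "upper endoscopy must have been performed no more than three months before time of diagnosis". For baseline data, "Age, sex and Charlson Comorbidity Index at date of primary upper endoscopy are derived from the National Patient Registry".

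**The concern.** Someone already taking an anti-reflux drug at endoscopy cannot start it. Their first dispensing afterwards is a continuation, and it will usually come early. The authors expect such patients, since earlier medication is a covariate in this same model.

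The covariate gives prior users their own average hazard, but the events inside that group remain a mixture of refills and real restarts. The model then estimates one common coefficient for age, sex, comorbidity, antithrombotic use and year across both kinds of event. A hazard ratio that readers will take to describe new treatment after diagnosis would partly describe who was already on treatment.

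The unstated time origin adds to this. If time runs from endoscopy, a drug first dispensed between endoscopy and diagnosis could count both as treatment before diagnosis and as the event.

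**Working it through.** The plan states no event rate, prior-user share or effect size, so there is no figure of its own to reproduce. What follows is illustrative.

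**Assumptions (none from the documents, except that the 2-year horizon matches the planned retrieval):**
- A binary factor x, split 50/50.
- Untreated patients with x = 0: 60% start within 2 years, so the hazard is −ln(0.40)/2 = 0.458 per year. With a true hazard ratio of 2, x = 1 has 0.916 per year, and 84% start.
- Prior users make up 25, 50 or 75% of the cohort. Some have lapsed and behave as untreated. The rest are continuing, with a median of 60 days to the next dispensing: hazard ln 2/(60/365.25) = 4.22 per year, whatever x is. Practically all have an event within 2 years.

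**Method.** Let g index the four cells of x by prior use u, with covariate vector z_g = (x, u), weighted survival S_g(t) and event density f_g(t). The large-sample Cox coefficients b = (b_x, b_u) solve

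∫₀² { Σ f_g z_g − [Σ z_g S_g exp(b·z_g) / Σ S_g exp(b·z_g)] Σ f_g } dt = 0.

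The prior-user cells are mixtures of lapsed and continuing patients, so a term for u cannot separate the two.

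**Share of events that are continuations.** At a true hazard ratio of 2, the average 2-year event risk in those not on drug is (0.60 + 0.84)/2 = 0.72. With 50% prior users, half of them lapsed, continuing users are 25% of the cohort, and the share is 0.25/(0.25 + 0.75 × 0.72) = 0.25/0.79 = 32%. At prior shares of 25, 50 and 75% it is 17, 32 and 45% with half lapsed, and 32, 58 and 81% with none lapsed.

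**Hazard ratio for x, adjusted for prior use:**

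| Lapsed among prior users, x=0 / x=1 | True HR | Prior share 25% | 50% | 75% |
|---|---|---|---|---|
| 0% / 0% | 2 | 1.60 | 1.33 | 1.14 |
| 50% / 50% | 2 | 1.80 | 1.64 | 1.51 |
| 75% / 75% | 2 | 1.90 | 1.81 | 1.72 |
| 75% / 50% | 1 | 1.13 | 1.25 | 1.35 |
| 75% / 50% | 2 | 2.04 | 2.07 | 2.09 |
| 25% / 75% | 2 | 1.44 | 1.08 | 0.85 |

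The first three rows assume that current use is unrelated to x, and there the bias is towards 1. In the last three it is related, and the bias can create an effect, inflate one or reverse one.

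A hand check shows why. Take the null factor with 75% lapsed at x = 0 and 50% at x = 1. At time zero the hazard among prior users is 0.75 × 0.458 + 0.25 × 4.22 = 1.40 for x = 0, and 0.50 × 0.458 + 0.50 × 4.22 = 2.34 for x = 1. The ratio is 1.67 with no effect on real starts.

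**Sensitivity to the inputs.** With 40 to 80% starting, the first row becomes 1.52–1.65, 1.26–1.38 and 1.11–1.17, and the second 1.74–1.84, 1.55–1.70 and 1.41–1.57. In the rows where current use is unrelated to x, medians of 30 or 90 days change the results by at most 0.03. Restricting to patients without prior use returns 2.00. A simulation of 60,000 patients (60% starting, 50% prior users, half lapsed) gave 1.62 against the limit of 1.64, and 1.97 after restriction.

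**The prior-use coefficient itself.** A separate simulation used 20,000 patients per scenario, prior users 20–60% of the cohort, 25–75% of them still on drug, and next dispensing uniform over days 1–100. With a true hazard ratio of 1.0 for prior use, the fitted value was 1.45–4.07: about 3–10 in the first 90 days and 0.96–1.04 after day 100. Removing patients still on drug gave 0.95–1.06.

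**The case against.** The strongest reply is that this is an undefined term, not a stated mistake. The plan says initiation, whose ordinary meaning excludes continuation, and it retrieves the history needed to apply that meaning. A reader might infer that the authors intend to count refills. The documents do not say so; they only fail to prevent it. Part of the objection fails, however: with prior users kept in the risk set and no rule for when they become able to initiate, the model as written cannot separate the two kinds of event.

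A second reply is that time to first treatment in all newly diagnosed patients is a coherent measure of care. That stands, and it is met by naming the endpoint accurately.

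A reader might also infer that the bias always dilutes effects, so that the results would be conservative. This holds only if the factor is unrelated to current use and does not affect refills. The Methods section makes the first condition doubtful for antithrombotics, because it retrieves those data to allow for preventive anti-secretory therapy. Dropping antithrombotic users, as the planned sensitivity analysis does, leaves the same question open for age, comorbidity and year.

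Finally, a reader might take the lack of a surgery-specific time model as part of the error. It is not. The primary model already separates surgery from drugs, and a Poisson analysis of treatment rates is planned.

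**Conclusion.** The point holds. The Cox model of initiation includes patients who may already be on treatment, sets no drug-free window, and can count refills as starts; the covariate for prior use does not repair this. That much follows from the text.

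The size does not. It depends on the share of prior users, how many are still on drug, and whether that differs by the factor studied, none of which is documented. Within the assumed range the distortion runs from slight (2.00 to 1.90) to a reversed direction (2.00 to 0.85), and a null factor can reach 1.35. No single direction should be claimed. The concern is confined to a secondary analysis and does not bear on the validity of the primary model. It is worth correcting because the correction is cheap.

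**What to change.** 1. Fit the initiation model in patients with no MA02B dispensing in the four-year look-back, ending the day before one stated index date. Endoscopy fits, because the baseline covariates are taken there. Censor at death and at 2 years.
2. Prespecify a shorter drug-free window (for example 1 year) as a sensitivity analysis, so that lapsed users can count as initiators.
3. If the all-patient model is kept, call its endpoint time to first dispensing or surgery after the index date, not initiation.

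A Cox model for surgery alone in all patients is an optional extra.

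**Cost.** SAP wording, one restricted model and one sensitivity run, using data already planned. If inclusion means the diagnosis date, the look-back before endoscopy could be up to three months short of four years, so the anchor must be stated.

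**Downsides.** The sample shrinks: 75, 50 or 25% of the cohort remains at prior shares of 25, 50 or 75%. A shorter window keeps 88, 75 or 63% if half of prior users have lapsed and pass it (1 minus half the prior share). The target population narrows. The prior-treatment covariate becomes constant and drops out of the restricted model; it can be estimated only in the all-patient model or, for lapsed users, in the shorter-window model. Entry at endoscopy is also conditional on a diagnosis up to three months later, which should be acknowledged.

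### The secondary census-based Poisson trend should use dispersion-scaled errors, with yearly diagnosis rates beside it and a stated year index (minor)

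*Combined protocol and SAP*

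**What the plan says.** The Statistical analysis section places the trend after the Cox model, among the secondary analyses: "Change in treatment rates over time will also be investigated using national Danish census data and Poisson regression". It does not give the variance estimator, the form of year (linear, curved or categorical), any age or sex strata, or the date that assigns a patient to a year.

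Three other parts of the document bear on it.

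- The Background gives US surgery rates per inhabitant that rise and then fall, and says of Denmark: "It is unknown whether Denmark follows the same trends". It also says that "it is currently unknown how many patients each year are given the diagnosis GERD after upper endoscopy in Denmark". No listed analysis estimates that number.
- The primary regression takes "treatment type (pharmacological, surgical or none) as primary outcome" and includes year of diagnosis among its independent variables.
- Under Methods, entry is fixed by endoscopy date: "Endoscopy must have been performed during the study period 2000-2015". Diagnosis may come later, since "upper endoscopy must have been performed no more than three months before time of diagnosis". Anti-reflux operations "performed within two years of inclusion are identified", and prescriptions are followed for the same two years.

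**The concern.** Poisson regression sets the variance of each yearly count equal to its mean. National yearly counts can also move together through changes in coding, capacity, prescribing habits or guidelines. That shared movement does not average out as counts grow, whereas Poisson noise shrinks relative to the count. The larger the series, the less shared variation is needed before ordinary year-to-year movement is reported as a trend. Drug treatment is more exposed than surgery for this reason.

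Two smaller matters affect how the result is read. Treated patients per inhabitant equals new diagnoses per inhabitant times the share treated, so the census rate can move, or stay flat, for either reason. And because entry is defined by endoscopy date, counting by another date leaves some years incomplete.

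**Working it through.** The plan gives no counts, dispersion, sample size or alpha for this analysis, so there is no figure of its own to reproduce. Every input below is an assumption unless a source is named.

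**1. Scale of the counts.** The Background cites an earlier Danish study in which "the rate of primary surgery was 5.2 per 100.000 inhabitants". With an assumed 5 to 6 million inhabitants, 5.2/100,000 × 5,000,000 = 260 and 5.2/100,000 × 6,000,000 = 312 operations a year nationally. The cohort holds a subset, so 50 to 200 a year is used for surgery. For drug treatment 1,000 to 5,000 a year is assumed.

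**2. False positives with model-based errors.** There are 16 yearly counts (2000 to 2015), a linear year and no true trend. Let n be the yearly mean and cv the extra yearly variation, independent between years.

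Dispersion φ = 1 + n × cv²; false-positive rate = 2 × [1 − Φ(1.96/√φ)].

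| n a year | cv | φ | Closed form | Simulated (20,000 runs) |
|---|---|---|---|---|
| 1,000 | 1% | 1.1 | 6.2% | 5.9% |
| 5,000 | 1% | 1.5 | 11.0% | 10.8% |
| 1,000 | 3% | 1.9 | 15.5% | 15.2% |
| 5,000 | 3% | 5.5 | 40.3% | 41.0% |
| 50 | 5% | 1.125 | 6.5% | 6.4% |
| 200 | 5% | 1.5 | 11.0% | 10.7% |
| 200 | 10% | 3.0 | 25.8% | 25.5% |

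With cv = 0 the rate is about 5% at every n. For surgery at cv = 3% it is only 5.7 to 7.1%.

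**3. With scaling.** Pearson-scaled errors and a t reference on 16 − 2 = 14 degrees of freedom give 4.7 to 5.4% for n from 50 to 5,000 and cv from 0 to 10%. This holds because the simulated years are independent. With correlation 0.5 between adjacent years:

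| n a year | cv | Plain Poisson | Scaled, t(14) |
|---|---|---|---|
| 200 | 10% | 0.40 | 0.17 |
| 5,000 | 3% | 0.56 | 0.20 |

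Scaling helps, but does not restore 5%.

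**4. Strata.** If the counts are split into S equal age and sex cells that share the yearly variation, dispersion measured across cells is 1 + (n/S) × cv², while the trend still carries 1 + n × cv². With n = 5,000, cv = 3% and, say, S = 20, the first is 1 + 250 × 0.0009 = 1.225 and the second 1 + 5,000 × 0.0009 = 5.5. Dispersion taken across cells would miss most of the problem.

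**5. Decomposition.** If diagnoses per inhabitant rise 3% a year and the share operated falls 3% a year, the census rate changes by (1.03 × 0.97)^15 = 0.99 over 15 years, against 0.97^15 = 0.63 per diagnosed patient. If diagnoses are constant, both are 0.63.

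**6. Year index, flat data.** By diagnosis date, year 2000 loses the fraction (mean lag in months)/12, because patients whose endoscopy was in 1999 are excluded.

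- Mean lag 0: no bias.
- Mean lag 0.5 month: 4.2% short, +0.09% a year.
- Mean lag 1.5 months (uniform over three months): 12.5% short, +0.28% a year, a factor of 1.043 over 15 years.
- Partial 2016 kept as a seventeenth year: −1.9% a year (lag 0.5 month) or −1.6% (lag 1.5 months).
- By date of surgery, the two-year window thins the first years: +1.0% a year (exponential delay, mean six months) to +2.3% (uniform over two years).
- By endoscopy date with full follow-up: no bias. If data stopped at the end of 2015: −1.1% to −2.3% a year, under the same two delay patterns.

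**The case against.** The strongest reply is that overdispersion is a general caution and not something found in this document. That is right: the text shows no extra variation, and the wide range in the table reflects the assumed inputs. It is also fair that the plan says only Poisson regression, so unscaled errors on yearly totals are one reading of it. Scaling is not a complete cure either. It assumes independent years, and with a straight line for year a real rise and fall, like that in the US series, would be counted as noise. These points stand and shape the remedy.

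A reader might infer that without a yearly diagnosis rate the study cannot tell more diagnosis from more treatment. The documents do not support that: the primary regression includes year of diagnosis and so already gives the per-patient trend. What is missing is the companion series that links that trend to the census rate. The +3%/−3% example is also chosen to cancel.

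A reader might also infer that the census denominator is wrong. It is a legitimate population rate for the Background's comparison with the US. Finally, the edge-year effect is small by diagnosis date and depends on an index the plan does not state.

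**Conclusion.** The point holds as a minor one, confined to a secondary analysis. Model-based Poisson errors on yearly national counts give no protection against extra variation. Under the assumed counts, the false-positive rate for drug treatment would be about 6 to 41% at 1 to 3% yearly variation, and about 5% with none. Quasi-Poisson errors are better in every overdispersed setting tried and cost little if the extra variation is absent. They reach the nominal level only when years are close to independent.

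The diagnosis series and the year index are lesser companions. The first fills a gap that the Background itself names. The second removes a bias of about 0 to 0.3% a year if years follow diagnosis date, the mean lag is at most 1.5 months and a partial 2016 is not kept; it would be larger if years followed treatment date. Nothing here shows that Danish counts are overdispersed, that the primary analysis is affected, or that the planned trend would mislead.

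**What to change.** State the following in the SAP.

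1. Fit the census-offset trend with dispersion-scaled (quasi-Poisson) errors and a t reference on the residual degrees of freedom, for surgery and drug treatment separately.
2. Allow for curvature in year, for example with a quadratic or spline term. A separate term for every year on yearly totals leaves no degrees of freedom for estimating dispersion.
3. If age and sex strata are planned, keep them, but take the dispersion from between-year variation. Patient-level robust errors do not capture it.
4. Check residuals for serial correlation, and interpret the p-value cautiously if it is present.
5. Report by year the new GERD diagnoses per adult inhabitant beside treated patients per adult inhabitant. Label the latter as a population rate limited to treatment within two years of a new diagnosis, to be read together with the primary model's year effect.
6. Index years by endoscopy date, and confirm that later diagnoses and the two-year treatment window are followed past 2015. Otherwise flag the incomplete first or last years.

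The cost is SAP wording and one table from the cohort and census data already planned; the plan should confirm that the extract runs past 2015. With a linear year, the t reference alone widens intervals by about 9% (2.145/1.960 = 1.094) when dispersion is estimated at 1, and further when it is higher. Each curvature term uses another degree of freedom, and the dispersion estimate rests on about 16 yearly points.

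### The census-based Poisson trend mixes how often GERD is newly diagnosed with how often it is then operated on, and its level is not comparable with the national rates cited in the Background

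*Combined protocol and SAP*

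**What the plan says.** The whole trend analysis is one sentence under Statistical analysis: "Change in treatment rates over time will also be investigated using national Danish census data and Poisson regression". It does not define the numerator, the time axis (year of diagnosis or year of operation), the date on which data end, or how the census figures enter.

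The available numerator has to be read from the Methods:

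- Population: "The study population consists of all adult Danish patients diagnosed with GERD and GERD-related diagnosis".
- Verification: "upper endoscopy must have been performed no more than three months before time of diagnosis for the patient to be included".
- Washout: "Patients with GERD and GERD-related diagnosis up to four years before upper endoscopy are excluded from the study".
- Period: "Endoscopy must have been performed during the study period 2000-2015".
- Surgery: operations under five procedure codes, "performed within two years of inclusion are identified".

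The Background gives surgery rates per inhabitant. The US rate is 16.7 per 100.000, falling to 6.1 in 2010. For Denmark in 1997-2005, "the rate of primary surgery was 5.2 per 100.000 inhabitants with a reoperation rate of 5" per cent. It adds: "It is unknown whether Denmark follows the same trends". The Aim, however, concerns newly diagnosed patients, and the gap named just before the Methods is how treatment has developed in that group.

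**The concern.** The denominator and the numerator belong to different questions. A census denominator suits a national surgery rate, but the operations described are only those that soon follow a new verified diagnosis. The numerator suits a question about newly diagnosed patients, but their treatment rate needs those patients as denominator. The planned combination is neither.

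Two misreadings could follow. A change in the number of people endoscoped and coded with GERD could be reported as a change in the use of surgery. And because the result has the same per-inhabitant form as the Background figures, readers will tend to set it beside them, although it counts only a subset of operations. The sentence covers medical treatment as well as surgery, and the first problem applies equally there.

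**Working it through.** The documents state no expected event count, rate or trend for this analysis, so there is no planned figure to reproduce. They also do not give the yearly number of new diagnoses, the chance of surgery, the share of all operations that the cohort captures, or the time from diagnosis to surgery. These are treated as assumptions below.

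**Step 1: what the rate measures.** For one year of diagnosis, let D be new verified diagnoses, S the operations within two years among them, and N the census population. Then S/N = (D/N) × (S/D). Only S/D describes treatment practice.

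- D/N up 50%, S/D unchanged: 1.5 × 1 = 1.5. Over the 15 yearly steps from 2000 to 2015 this is 1.5^(1/15) = 1.027 per year, with no change in practice.
- D/N down by one third, S/D unchanged: 0.667, or 0.667^(1/15) = 0.973 per year.
- D/N up 50%, S/D down by one third: 1.5 × 0.667 = 1.00. A real fall in the use of surgery is hidden.

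Movement in D/N is plausible on the protocol's own account: the Background says that GERD prevalence has been rising, and that the yearly number diagnosed after endoscopy in Denmark is unknown.

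**Step 2: level.** Let c be the share of all primary operations that meet the cohort and two-year rules. An unchanged national rate of 5.2 would appear as 5.2 × c.

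| Assumed c | Rate per 100.000 | Gap to 5.2 |
|---|---|---|
| 0.9 | 4.68 | -10% |
| 0.7 | 3.64 | -30% |
| 0.5 | 2.60 | -50% |
| 0.3 | 1.56 | -70% |

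This is a difference in level from an outside figure. It is not a trend, and its size rests wholly on c.

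**Step 3: trend within the series, true rate flat.** Diagnoses were simulated evenly over 2000-2015, with time to surgery inside the two-year window either uniform or front-loaded (truncated exponential, scale 0.7 years). A log-linear Poisson model was then fitted to the yearly counts. The total change is the yearly ratio raised to the 15th power, or the 17th for 2000-2017, minus 1.

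| Counting rule | Uniform: ratio per year (total) | Front-loaded: ratio per year (total) |
|---|---|---|
| Year of diagnosis, full two years for all | 1.000 (0%) | 1.000 (0%) |
| Year of diagnosis, data end 31 Dec 2015 | 0.978 (-29%) | 0.987 (-18%) |
| Year of operation, 2000-2015 | 1.023 (+41%) | 1.013 (+21%) |
| Year of operation, 2000-2017 | 1.000 (0%) | 0.984 (-23%) |

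The artefacts come from partly filled edge years. In the uniform case, a data end in 2015 leaves 75% of the 2014 operations and 25% of the 2015 operations visible. Counting by year of operation instead leaves 2000 at 25% and 2001 at 75% of the steady level (50% and 92% if front-loaded).

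**Step 4: the series as a proxy for the national trend.** A constant c cancels from the yearly ratio, whatever its value. A drifting c does not. With a flat national rate, c moving from 0.6 to 0.4 gives 0.974 per year (0.4/0.6 - 1 = -33%), and c moving from 0.4 to 0.6 gives 1.027 per year (0.6/0.4 - 1 = +50%).

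**The case against.** The strongest defence is that the study never undertakes to measure national surgery. Its title, Aim and stated gap concern newly diagnosed patients, and the US and Danish rates are context. A per-patient trend is also already planned, since year of diagnosis enters the logistic and multinomial models of treatment type and the Cox model of time to treatment. The census-based rate could then be a legitimate secondary description of how often newly diagnosed GERD is treated each way in the population. Finally, the trend sentence does not define its numerator, so the restriction is inferred from the data description.

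Much of this stands. The Aim is not the national rate, the per-patient trend is available elsewhere in the plan, and the numerator is an inference, although no other surgery data are described. But the other models do not correct the Poisson result. It is labelled as change in treatment rates, it can move against those models because of diagnosis frequency alone, and the plan does not say how such a disagreement would be read.

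A reader might go further and infer that the analysis must show a false fall in Danish surgery, of 30% to 70% for instance. The documents do not support that. Those percentages are level gaps that follow from assumed values of c, and they become a fall only if the cohort series is joined to the 1997-2005 figure, which no section plans. Within the series a constant c gives no false trend, and one permitted counting rule gives a false rise.

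**Conclusion.** The point holds as a mismatch between numerator and denominator, together with an incomplete definition. On the data described, the census-based Poisson trend for surgery is the product of diagnosis frequency and treatment choice, so a change in it cannot be attributed to treatment practice. Any proportional change in diagnoses per inhabitant passes straight into the reported rate.

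Its level is not comparable with 16.7, 6.1 or 5.2 per 100.000, and on its own it cannot settle whether Denmark follows the US pattern. Follow-up and calendar-edge effects can add an artefact in either direction, from about -29% to +41% over the period under the two time-to-surgery shapes assumed, or none if patients are counted by year of diagnosis with complete two-year follow-up.

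The capture share, its drift, the change in diagnoses and the time to surgery are all assumptions. The identity in Step 1 needs none of them. The logistic, multinomial and Cox analyses are unaffected, so this is a worthwhile correction to a secondary analysis and not a flaw in the main one.

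**What to change.** 1. For treatment rates over time, run the Poisson model by year of diagnosis, with the number of newly diagnosed patients, or their person-years over a full two-year follow-up, as the offset. Define the numerator for surgery and for medical treatment, and state the data-end date. If the registers do not cover two full years for the last patients included, limit the trend to diagnosis years that have them.
2. Keep the census denominator for the incidence of new endoscopy-verified GERD, which answers the protocol's own question about yearly numbers. Shown side by side, the two series separate the components of Step 1.
3. State that cohort figures are not compared with the per-inhabitant rates in the Background.

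These three changes use data already planned and cost only wording, provided that the extract covers the full two-year window.

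4. Only if the Background's national question is to be answered, add a separate series: all first adult operations under the same five codes by calendar year of operation, over the adult census population. The cost is a wider register extract, covered by the data permissions, and one more model. Comparison with the cited rates would still need caution, because the documents do not give the age limits or procedure codes behind them.
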